4.1. Primary Efficacy Endpoint

Primary Endpoint:

- Percentage of patients on SEL-212 vs. KRYSTEXXA® who achieve and maintain reduction of SUA < 6 mg/dL for at least 80% of the time during Treatment Period 3 and Treatment Period 6.

Serum samples for measurement of SUA will be collected according to the schedules described in section 3.8 tables B and D.

4.2. Secondary Efficacy Endpoints

Secondary Endpoints:

- Reduction of mean SUA in patients on SEL-212 vs. KRYSTEXXA® as computed by subtracting baseline SUA level from the mean SUA (area under the SUA time curve) during Treatment Period 3 and Treatment Period 6
- Percent reduction of mean SUA in patients on SEL-212 vs. KRYSTEXXA® as computed as the mean SUA level during treatment period (area under the SUA time curve) minus baseline SUA level divided by baseline SUA level multiplied by 100 during Treatment Period 3 and Treatment Period 6
- Percentage of patients on SEL-212 vs. KRYSTEXXA® who achieve and maintain reduction of SUA < 6 mg/dL for at least 80% of the time during Treatment Period 6
- Percentage of patients on SEL-212 vs. KRYSTEXXA® who achieve and maintain reduction of SUA < 6 mg/dL for 100% of the time during Treatment Period 6
- Reduction of mean SUA in patients on SEL-212 vs. KRYSTEXXA® as computed by subtracting baseline SUA level from the mean SUA (area under the SUA time curve) during Treatment Period 6
- Percent reduction of mean SUA in patients on SEL-212 vs. KRYSTEXXA® as computed as the mean SUA level during treatment period (area under the SUA time curve) minus baseline SUA level divided by baseline SUA level multiplied by 100 during Treatment Period 6
- Percentage of patients who achieve and maintain reduction of SUA < 6 mg/dL for at least 80% of the time during Treatment Period 3
- A summary table of the number and percentage of patients who achieve and maintain reduction of SUA < 6 mg/dL for 100% of the time during Treatment Period 3 will be provided by treatment group.
- Reduction of mean SUA in patients on SEL-212 vs. KRYSTEXXA® as computed by subtracting baseline SUA level from the mean SUA (area under the SUA time curve) during Treatment Period 3
- Percent reduction of mean SUA in patients on SEL-212 vs. KRYSTEXXA® as computed as the mean SUA level during treatment period (area under the SUA time curve) minus baseline SUA level divided by baseline SUA level multiplied by 100 during Treatment Period 3
- Percent of patients on SEL-212 vs. KRYSTEXXA® in pre-dose SUA values > 6 mg/dL during Treatment Periods 2-6. The pre-dose SUA is collected on the dosing day prior to the dosing administration or it is collected at the visit where dosing would have occurred had the patient not

This document is confidential.

Statistical Analysis Plan

Sponsor: Selecta Biosciences

Protocol No.: SEL-212/202

been previously withdrawn from study drug for those patients who have been withdrawn from study drug.

- Change in health questionnaires to end of treatment period 3 and 6:
 - Health Assessment Questionnaire-Disability Index (HAQ-DI)
 - The Provider Global Assessment of Disease Activity (PrGA)
 - Short Form Health Survey 36 (SF-36)
- Percent of patients on SEL-212 vs. KRYSTEXXA® of gout flare incidence per 3-month period (Treatment Periods 1-3 and Treatment Periods 4-6)
- Percent of patients on SEL-212 vs. KRYSTEXXA® of gout flare frequency per 3-month period (Treatment Periods 1-3 and Treatment Periods 4-6)
- Change from Baseline to Treatment Period 6 in number of tender joints
- Change from Baseline to Treatment Period 6 in number of swollen joints

4.3. Safety Endpoints

Safety Endpoints:

- Safety and tolerability of SEL-212 compared to KRYSTEXXA® as assessed by AEs, serious AEs (SAEs), deaths, and discontinuations due to AEs

Additional safety assessments will include review and evaluation of laboratory testing including hematology, coagulation, chemistry, urinalysis; vital signs; 12-lead ECGs; and physical examination findings.

This document is confidential.

5. Analysis Sets

5.1. Screened / Randomized Set

The Screened Set will include all patients who signed an informed consent. The Randomized Set will include all patients who were randomized.

5.2. Safety Set

The Safety Set (SS) will include all patients who were administered any amount of study medication. Patients will be analyzed according to treatment received. The SS will be used for all analyses of safety endpoints and for the presentation of patients in all patient listings.

5.3. Intent-to-Treat Set

The Intent-to-Treat (ITT) Set will be used as the primary population for the analysis of efficacy. The ITT Set will include all randomized patients. Patients will be analyzed according to randomized treatment. ITT set is same as randomized set by its definition and will be referred as so in this SAP.

5.4. Modified Intent-to-Treat

The modified ITT (mITT) Set will include all randomized patients who were administered at least one complete dose of study medication and have at least one post-baseline assessment of SUA. Patients will be analyzed according to randomized treatment. The mITT will also be used for analyses of efficacy endpoints.

5.5. Per Protocol Set

The Per Protocol (PP) Set will include all patients who 1) were administered any amount of study medication, and 2) have completed at least 65% of the study dosing visits with or without receiving study drug (eg at least 4 of 6 TP Day 0 visits for patients receiving SEL-212 or at least 8 of 12 TP Day 0 or Day14 visits for patients receiving Krystexxa) unless early termination from the study occurred after study drug withdrawal due to meeting stopping rules or due to an adverse event, or due to PI discretion (for example where at least one pre-dose SUA was >6 mg/dL in the Krystexxa arm and patient was discontinued from study treatment), and 3) who have no major Protocol deviations affecting the primary efficacy assessments. Patients will be analyzed according to randomized treatment.

5.6. Protocol Deviations

All protocol deviations related to study inclusion or exclusion criteria, conduct of the trial, patient management, dosing, and sampling procedures or patient assessment will be listed. The list of protocol deviations will be reviewed by the Sponsor, the principal investigator, the study statistician and the study pharmacokineticist and finalized before database lock. Determination of whether the deviation is major or minor, or has impacts on primary efficacy assessment will be based on the biasing impact of the deviation on the safety and efficacy data. Major protocol deviations affecting the primary efficacy assessments include: 1) major protocol deviations that lead to premature study drug discontinuation; 2) major protocol deviations that lead to patients receiving study drug treatment in treatment periods 3 or 6 that they would not otherwise have received (such as incorrect application of the protocol stopping rules that allow a patient to continue dosing despite having met the stopping criteria); and 3) protocol deviations that involve out of window sampling of SUA due to a) visits occurring outside of the protocol visit window for dosing days (where dosing days refer to dosing visits of patients still on study drug who have not previously been withdrawn from study drug) in Treatment period 3 and 6, b) visits occurring outside of the protocol visit

This document is confidential.

window for visits within TP3 or TP6 scheduled 1 week prior to the dosing days, c) visits occurring outside of the protocol visit window for TP6 D21 for patients who have not been withdrawn from study drug and for dosing day TP4D0, or d) visits occurring 35 days or more beyond TP6D0 for the TP6D28 visit for patients who have not been withdrawn from study drug, where the protocol visit window above refers to the current protocol window allowed at the time of analysis. Major protocol deviations affecting the primary efficacy assessments will be reviewed and determined periodically during clinical and medical review of protocol deviations during the study.

Protocol deviations related to Covid-19 will be identified and flagged.

5.7. General Methods

SAS® version 9.4 or higher will be used for all statistical analyses and tabulations.

In general, summaries will present data by treatment group and assessment time where appropriate.

Unless stated otherwise, descriptive summaries will include n, mean, standard deviation, median, minimum and maximum for continuous variables, and n and percent for categorical variables. If there are multiple assessments collected on the same scheduled time within the visit windows defined for each assessment, the average of these assessments will be used. For tabulated safety summaries, only the scheduled assessments will be included in the summary tables.

Data collected at unscheduled visits will be included in the data listings but will not be included in the analyses or by treatment summaries.

Adverse events and medical history will be coded according to the most recent version of Medical Dictionary for Regulatory Activities (MedDRA). Prior and concomitant medications will be coded using the most recent WHO Drug Dictionary version. The actual version of MedDRA and WHO drug used will be noted on the corresponding actual output.

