10.6 Administration

10.6.1 SEL-212

Before administration of SEL-212, patients will be premedicated with antihistamines and steroids as described in [Section 10.5](#).

Patients will receive treatment with SEL-212 on Day 0 of each Treatment Period for a total of 6 doses of study drug.

All study drugs should be administered through the same IV access. All blood samples should be drawn from an alternative venous access.

If an infusion reaction occurs, Investigators are permitted to use concomitant medications or treatments deemed necessary to provide adequate patient care. Investigators should also utilize the infusion reaction lab kit provided in the Study Operations Manual to collect additional blood specimens. In the case of a Grade 3 or 4 infusion reactions occurring during an infusion, the administration of study drug should be immediately discontinued, and the affected patient should be treated according to the clinical trial site's protocol for infusion reactions (e.g., monitoring, administration of antihistamines, corticosteroids, fluids and epinephrine, as clinically indicated).

The reconstituted SEL-110.36 will be withdrawn from the vial and dosed via IV infusion with a syringe infusion pump utilizing an appropriately sized syringe. SEL-110.36 will be infused at a rate of 3.0 mL/hr for the first 30 minutes, then a rate adequate to deliver the remaining dose volume over a period of 60 minutes concurrently with 125 mL normal saline. Following the infusion of SEL-110.36, the main IV line must be flushed with normal saline prior to the start of the SEL-037 infusion. Refer to the Study Operations Manual for instructions regarding infusions for patients with medical history involving cardiovascular comorbidities.

SEL-037 infusion will start within 15 minutes after completion of the SEL-110.36 infusion. SEL-037 will be infused via infusion pump over a time period of no less than 120 minutes. If an infusion reaction occurs during the administration of SEL-037, the infusion may be slowed, or stopped and restarted at a slower rate at the discretion of the physician. Following the infusion of SEL-037, the main IV line must be flushed with normal saline.

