7.1. Primary Efficacy Endpoint Analysis

The primary efficacy endpoint is defined as:

- Comparison in the percentage of patients on SEL-212 vs. KRYSTEXXA® who achieve and maintain reduction of SUA < 6 mg/dL for at least 80% of the time during Treatment Period 3 and Treatment Period 6

The SUA time curve will be used to estimate the proportion of time that the SUA level is below 6 mg/dL. Based on the serum samples collected during Treatment Periods 3 and 6, an estimate of the time with SUA < 6 mg/dL can be determined by connecting each two neighboring data points with a straight line. SUA values collected at unscheduled visits within period 3 and period 6 will be included for the SUA time curve. If the SUA time curve goes above 6 mg/dL the linear interpolation method will be used to estimate the point in time at which the SUA time curve intercepts the line between the last SUA value < 6 mg/dL and the first value \geq 6 mg/dL.

The proportion of time that the SUA level is < 6 mg/dL will be computed by taking the ratio between the time during which the SUA level remains < 6 mg/dL (if necessary, using the linear interpolation method) and the entire time interval within Treatment Periods 3 and 6. For period 3, entire time interval is between time of day 0 SUV assessment for period 3 and period 4. For Period 6, the entire time interval is between time of day 0 and day 28 assessment.

Let T1 be the total time interval in hours for Treatment Period 3 of which W1 hours is the time interval during which SUA level is < 6 mg/dL. Similarly, for Treatment Period 6, assume T2 is the total time interval in hours of which W2 hours is the time interval during which SUA level is < 6 mg/dL. For a patient to be considered a responder, the proportion of time that the SUA level is < 6 mg/dL during Treatment Periods 3 and 6 must be at least 80%. The proportion of time that the SUA level is < 6 mg/dL, i.e., percentage (p) of non-hyperuricemic time, is calculated using the following formula:

$$\text{Percentage (p)} = \frac{W1 + W2}{T1 + T2} \times 100$$

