8.4. Laboratory Evaluations

Laboratory data will be summarized by the type of laboratory test and will be presented for each scheduled visit by treatment group (SEL-212 or KRYSTEXXA®). Normal reference ranges and markedly abnormal

This document is confidential.

results will be used in the summary of laboratory data. Data will be flagged according to the reference limits (High or Low), if applicable. Changes from baseline will be presented for each post-baseline visit. Shift tables of the number of patients with low/normal/high values at each scheduled post-baseline visit compared to the low/normal/high categorization at baseline will be provided by treatment group (SEL-212 or KRYSTEXXA®).

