8.6. ECG

For each 12-lead ECG variable the actual value and the change from baseline will be summarized for the scheduled visits by treatment group (SEL-212 or KRYSTEXXA®).

Frequency tables of abnormal clinically significant evaluations as well as the number and percentage of patients with noteworthy QTcF/QTcB values (> 450 , > 480 and > 500 ms) and of patients with noteworthy QTcF/QTcB changes from baseline (≥ 30 but < 60 ; ≥ 60 ms) will be provided.

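### SAP 5.7 keeps unscheduled lab and ECG results out of the shift, markedly abnormal and QTc tables and averages same-time repeats, with no worst post-baseline summary to offset this

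*SAP*

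**What the plan says.** SAP 5.7 (General Methods) sets three rules that together decide which safety values are tabulated.

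- On unscheduled visits: "Data collected at unscheduled visits will be included in the data listings but will not be included in the analyses or by treatment summaries".
- On safety tables: "For tabulated safety summaries, only the scheduled assessments will be included in the summary tables".
- On repeats: for "multiple assessments collected on the same scheduled time within the visit windows defined for each assessment, the average of these assessments will be used".

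The safety sections apply these rules without exception. SAP 8.4 plans "Shift tables of the number of patients with low/normal/high values at each scheduled post-baseline visit", plus a summary using reference ranges and markedly abnormal results, for which it gives no limits. SAP 8.6 plans the "number and percentage of patients with noteworthy QTcF/QTcB values" above 450, 480 and 500 ms, and changes from baseline of 30 to under 60 ms and of 60 ms or more. Protocol 13.5.3 and 13.5.5 describe the same laboratory and ECG tables. Neither document defines a table based on each patient's worst post-baseline value.

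For efficacy, SAP 7.1 makes its own provision for serum uric acid (SUA): "SUA values collected at unscheduled visits within period 3 and period 6 will be included for the SUA time curve".

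**The concern.** By-visit means belong on scheduled values. Outlier tables have a different job: to show how many patients ever crossed a limit after starting treatment. A test ordered because a patient is unwell is more likely than a routine one to catch an extreme value, and it is usually unscheduled. If outlier tables take only scheduled values and average any repeats, they can understate how many patients had a marked laboratory change or a long QTc. A reader of those tables alone could take a low count as reassurance when the plan simply did not look at the relevant results.

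**Working it through.** The documents state no figure on this point, so there is none to reproduce. The check has four steps.

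**1. Scheduled opportunities for a completer (Protocol Appendices A and C; SAP 3.8 Tables A and C).**

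- ECG: Screening, Treatment Period 6 Day 28 and early termination. That is at most one scheduled post-baseline ECG per patient.
- Chemistry and hematology: Day 21 (SEL-212) or Day 14 (KRYSTEXXA) of each of six periods, plus Treatment Period 6 Day 28. That is 6 + 1 = 7 post-baseline draws in either arm.

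**2. Timing relative to dosing.** Treatment lasts 168 days, and the last scheduled infusion is on Study Day 140 (SEL-212) or 154 (KRYSTEXXA) (Protocol 7.1).

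- A completer's single ECG falls nominally 168 − 140 = 28 days after the last SEL-212 infusion, or 168 − 154 = 14 days after the last KRYSTEXXA infusion.
- A patient withdrawn from drug continues visits to the end of Treatment Period 6 (Protocol 7.4.1), so the interval can be longer. A SEL-212 patient stopped on the first Day 21 result was last dosed on Day 0, and the ECG comes nominally 168 days later.
- Dosing-day laboratory samples are taken before infusion (Protocol 7.1.2). Nominally, therefore, no scheduled draw falls sooner than 14 days after a dose in either arm.

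A transient abnormality inside these intervals can be seen only through unscheduled testing, which SAP 5.7 sends to the listings.

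**3. Effect of averaging repeats at one scheduled time.** Mean = sum / number of readings. The readings are illustrative; the QTc limits are those of SAP 8.6.

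| Readings | Category of highest reading | Mean | Category tabulated |
|---|---|---|---|
| QTc 505, 470 ms | >500 | 487.5 | >480 |
| QTc 485, 470 ms | >480 | 477.5 | >450 |
| QTc 455, 440 ms | >450 | 447.5 | not counted |
| QTc 510, 495 ms | >500 | 502.5 | >500 (unchanged) |
| Lab 1.3, 0.6 × ULN | High | 0.95 | not High |
| Lab 1.6, 0.9 × ULN | High | 1.25 | High (unchanged) |

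Averaging can lower a category but does not always do so. It applies only to repeats at the same scheduled time within the visit window. If the repeat is at an unscheduled visit, it is excluded and the scheduled value is tabulated as measured.

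**4. Effect of exclusion, as an assumed range.** The documents give no count of unscheduled results. Assume 75 patients per arm (the planned number), all assessed, of whom k = 4 to 12 have a true post-baseline abnormality, seen only at an unscheduled visit in a share s = 25% to 75% of them. Tabulated percentage = k(1 − s)/75.

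- k = 4: true 4/75 = 5.3%; tabulated 3/75 = 4.0% (s = 25%) down to 1/75 = 1.3% (s = 75%).
- k = 12: true 12/75 = 16.0%; tabulated 9/75 = 12.0% (s = 25%) down to 3/75 = 4.0% (s = 75%).

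These figures show how the rule behaves. They are not an estimate for this trial.

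**The case against.** The strongest reply is that these abnormalities have another route into the tables. Protocol 12.2.2.6 makes clinically significant laboratory, ECG and vital-sign findings in dosed patients adverse events, whenever they are found. Protocol 12.2.1.5 adds clinically significant hyperlipidemia, worsening renal function tests, proteinuria and leukopenia as events of special interest. SAP 8.3 tabulates treatment-emergent events, including by maximum intensity. This stands as a partial offset. It relies on investigator judgement in an open-label trial, gives no numeric shift or QTc category, and QTc is not among the listed events of special interest.

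Two further objections also stand and shape the fix. Protocol 13.5.3 itself specifies shift tables by scheduled visit, so replacing them would depart from the protocol; adding a table would not. For-cause testing is unblinded and may differ between arms, whereas scheduled laboratory draws are matched at seven each, so a worst-of-all-values comparison could carry ascertainment bias.

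A reader might also infer more than the text supports:

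- *That worst values never reach any table.* They can: a single value at a scheduled visit counts as measured, early termination is a schedule column with labs and an ECG, and the adverse event tables capture some cases.
- *That averaging hides values above 3 × ULN.* That limit appears only as an eligibility criterion. SAP 8.4 flags values against reference limits, and a mean of 2.9 × ULN would still be High.
- *That infusion-reaction results are lost from the shift tables.* Protocol 10.6.1 says "Investigators should also utilize the infusion reaction lab kit provided in the Study Operations Manual to collect additional blood specimens", but neither document says which analytes the kit measures.
- *That SAP 5.7 and 7.1 conflict over SUA.* SAP 7.1 is a specific, explicit rule for one endpoint and governs over a general-methods sentence. Only a cross-reference is missing.

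**Conclusion.** The point holds for the laboratory shift, markedly abnormal and QTc-category tables, and no further. Following the plan as written, an abnormality seen only at an unscheduled visit cannot be counted in those tables, and one of several readings at the same scheduled time can be averaged below a limit. The effect is greatest for QTc, with one scheduled post-baseline ECG, nominally 14 days (KRYSTEXXA) or 28 days (SEL-212) after the last planned infusion.

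The size is unknown: it depends on how many unscheduled and repeat results exist, which the documents do not say. It might be inferred that the comparison between arms is biased towards no signal. The documents support only that counts within these tables can be too low. The direction of any bias between arms would depend on how for-cause testing is distributed. This does not touch the primary analysis. It is a change worth making before database lock.

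**What to change.** - Keep the by-visit summaries and by-scheduled-visit shift tables as the protocol specifies.
- Add to SAP 8.4 a worst post-baseline table: shift from baseline to worst value, and patients with any markedly abnormal value, with the limits for markedly abnormal written down.
- Add to SAP 8.6 a table of each patient's worst post-baseline QTcF and QTcB value and change, in the existing categories.
- Derive both from all scheduled, unscheduled, repeat and early-termination values, without averaging.
- Amend SAP 5.7 to permit this, and add an editorial cross-reference to the SUA rule in 7.1.
- Present the new tables beside the scheduled-only ones, with a note that for-cause testing may differ between arms in an open-label trial.

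The cost is SAP wording and a worst-value flag in each data set, with no new data. Abnormality counts may look slightly less favourable. Protocol section 13 allows the SAP to add exploratory analyses, so the addition fits the existing framework. It cannot make up for the sparse ECG schedule; it recovers only ECGs that were done anyway.

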5.8. Key Definitions

Baseline is defined as the last non-missing value prior to the start of infusion of SEL-212 or KRYSTEXXA®.

Day 0 of Treatment Period 1 is defined as the first date of study drug administration.

Study day within each treatment period will be calculated as date of event/collection – first dose date at each treatment period to be consistent with protocol defined day 0.

Overall study day will be calculated as date of event/collection – first dose date of the study.

